## 3.2 General study level definitions

### 3.2.1 Analysis time points

#### 3.2.1.1 First and last dose of LCM

Unless otherwise noted, all references to the first dose of LCM in this SAP refer to the first dose of LCM during EP0034 (ie, not the first dose of LCM from the previous study in which subjects participated prior to EP0034). Unless otherwise noted, all references to the last dose of LCM in this SAP refer to the last dose of LCM in the study.

#### 3.2.1.2 Relative day

Relative day will be calculated as the current date minus the date of first dose of LCM plus 1 for days on or after the day of first dose of LCM and prior to or on the day of last LCM dose (eg, the day of first dose will be Day 1). For days prior to the first dose of LCM (the day prior to first dose will be Day -1), relative day will be calculated as the current date minus the date of first dose of LCM. For days after the last dose of LCM, relative day will be calculated as the current date minus the date of last dose of LCM including a "+" to denote post-treatment days (eg, the day after the last dose will be Day +1). Relative day will not be calculated for partial or missing dates.

### 3.2.2 Study periods

This study consists of a Treatment Period and a Post-Treatment Period.

#### Treatment Period

This is defined as the period of time from the date of first dose of LCM in EP0034 to the latter of the last LCM dose date and the study Termination Visit date.

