4.2.2 Secondary efficacy variable

The secondary efficacy variable planned for analysis will be based on seizure diary data from EP0034 and will include the following for all subjects:

- Percentage of seizure-free days during the study (presented for the overall Treatment Period only)

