At the completion of the study, investigators should discuss treatment options with the subject and/or their legal representative(s) to best manage the subject's epilepsy. Taper of LCM may not be required for some subjects who complete the study, depending on the treatment option selected by the investigator in consultation with the subject and/or legal representative(s). These subjects should complete Visit 13/Termination Visit and then complete the Safety Follow-Up Telephone Contact 30 days (-1/+3 days) after the final dose of LCM. The Safety Follow-Up Visit is not required for subjects who complete the study and who do not undergo taper of LCM. The Safety Follow-Up Visit and the Safety Follow-Up Telephone Contact are not required for subjects who participate in EP0151 or EP0152.

Subjects who complete the study and discontinue use of LCM (as determined by the investigator in consultation with the subject and/or legal representative) should enter the Taper Period after the Visit 13/Termination Visit and taper LCM gradually as described in Section 7.2.2. A Taper Visit will be performed at the end of the Taper Period, followed by the Safety Follow-Up Visit that occurs 2 weeks (± 2 days) after the final dose of LCM, and then the Safety Follow-Up Telephone Contact that occurs 30 days (-1/+3 days) after the final dose of LCM.

Lacosamide for taper will be dispensed only for subjects who achieve a dose of LCM ≥ 3 mg/kg/day for subjects receiving oral solution, or LCM ≥ 150 mg/day for subjects taking tablets (Section 7.2.2). It is recommended that the dose be tapered gradually in weekly decrements. A slower taper is permitted, if medically necessary. In case of an emergency, a faster taper is permitted after discussion with the Medical Monitor, whenever possible.

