- PedsQL assessment (form consistent with age at the visit; however, the form used in the primary study must be used for at least 1 year after the Baseline assessment of the primary study, as described in Section 9.3)
- Contact IXRS (only if LCM will be dispensed for taper, as described below)
- Review LCM return and compliance
- Dispense LCM (if applicable for taper, as described below)
- Reminder to complete subject diary on a daily basis
- Adverse event reporting
- Health care resource use

At the time of withdrawal from the study, investigators should discuss treatment options with the subject and/or their legal representative(s) to best manage the subject's epilepsy. Taper of LCM may not be required for some subjects who withdraw from the study prematurely, depending on the treatment option selected by the investigator in consultation with the subject and/or legal representative(s). These subjects should complete the Early Termination Visit and then complete the Safety Follow-Up Visit 2 weeks (± 2 days) after the final dose of LCM, followed by the Safety Follow-Up Telephone Contact 30 days ($-1/+3$ days) after the final dose of LCM.

Subjects who withdraw from the study prematurely and discontinue use of LCM (as determined by the investigator in consultation with the subject and/or legal representative) should taper LCM gradually as described in Section 7.2.2. These subjects should complete the Early Termination Visit and enter the Taper Period. A Taper Visit will be performed at the end of the Taper Period, followed by the Safety Follow-Up Visit 2 weeks (± 2 days) after the final dose of LCM, and then the Safety Follow-Up Telephone Contact 30 days ($-1/+3$ days) after the final dose of LCM.

Lacosamide for taper will be dispensed only for subjects who achieve a dose of LCM ≥ 3 mg/kg/day for subjects receiving oral solution, or LCM ≥ 150 mg/day for subjects taking tablets (Section 7.2.2). It is recommended that the dose be tapered gradually in weekly decrements. A slower taper is permitted, if medically necessary. In case of an emergency, a faster taper is permitted after discussion with the Medical Monitor, whenever possible.

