9 ASSESSMENT OF EFFICACY

9.1 Seizure frequency

Efficacy variables based on seizures will be measured using data obtained from subject diaries. If an electronic diary was used in the primary study, the subject will continue to use the same diary in EP0034; otherwise, a new diary will be dispensed at admission to EP0034. Subjects or their caregivers will keep a diary to record the daily seizure activity from the beginning of the Treatment Period (Visit 1) until the last study visit, recording both seizure type and seizure frequency. The seizure records will be checked by the investigator with regards to correct and thorough daily completion by the subject, and to determine if a dose adjustment is required. At each visit and telephone contact subject and/or legal representative should be reminded to complete subject diaries on a daily basis.

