#### Taper Period

The Taper Period (up to 4 weeks, depending on dose level achieved) will be required for subjects who complete the study or withdraw from treatment during the study if the following doses are achieved: LCM  $\geq 3$ mg/kg/day for subjects receiving oral solution, or LCM  $\geq 150$ mg/day for subjects taking tablets; lower doses will not require a taper. Taper of LCM may not be required for some subjects who complete the study or withdraw from the study prematurely, depending on the treatment option selected by the investigator in consultation with the subject and/or legal representative(s) or for subjects who participate in EP0151 or EP0152.

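### For subjects who taper, the SAP counts the Taper Period as Treatment Period without declaring it, so taper diary days enter the only secondary efficacy variable and the other seizure summaries

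*SAP*

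**What the plan says.** SAP 3.2.2 sets up two analysis periods: "This study consists of a Treatment Period and a Post-Treatment Period". Treatment runs from the first EP0034 dose "to the latter of the last LCM dose date and the study Termination Visit date". SAP 3.2.1.1 adds that, unless noted, "all references to the last dose of LCM in this SAP refer to the last dose of LCM in the study". Taper doses are not excepted, and Protocol 8.3 counts them when fixing the final dose.

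The protocol keeps the taper apart. Completers who stop lacosamide (LCM) "should enter the Taper Period after the Visit 13/Termination Visit and taper LCM gradually as described in Section 7.2.2" (Protocol 8.1.12). For those who withdraw and stop, Protocol 8.1.13 says: "These subjects should complete the Early Termination Visit and enter the Taper Period". SAP 2.3 gives the taper its own heading: "The Taper Period (up to 4 weeks, depending on dose level achieved) will be required for subjects who complete the study".

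The only secondary efficacy variable is "Percentage of seizure-free days during the study (presented for the overall Treatment Period only") (Protocol 4.2.2, repeated in SAP 2.2.3.2). Diaries start at Visit 1 and run "until the last study visit, recording both seizure type and seizure frequency" (Protocol 9.1). Protocol 8.2 has a diary reminder at the Taper Visit. Under Protocol 8.3, subjects who enter safety follow-up return the diary at the Safety Follow-Up Visit.

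SAP 3.2.20 and 4.2.5 use every diary day with data. SAP 9.1.3 admits a subject to an interval on any seizure data, with no minimum. SAP 3.9 lists two changes from the protocol: added subgroups and fewer 3-month adverse event tables.

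**The concern.** The SAP computes the secondary variable over a period that is wider, for subjects who taper, than the one the protocol calls the Treatment Period, and it does not say so. Taper days are days of planned dose withdrawal, yet they would be read as evidence on maintained treatment.

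The window also depends on what follows the study. Subjects who stay on LCM, enter EP0151 or EP0152, or are below the taper threshold contribute no taper days. Two subjects treated for the same time can therefore be measured over different periods.

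The interval tables are more exposed than the overall figure. A subject who has left can appear in a later responder interval on taper data alone. The ≥24-month interval, which reads as the longest-term result, can consist mainly of taper days.

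**Working it through.** **Inputs**
- A month is 28 days and the first dose is Day 1 (SAP 3.2.5).
- Seizure intervals end at 3, 6, 12, 18 and 24 months, and the last is ≥24 months (SAP 3.2.21).
- Visit 13 is at Week 96, ±7 days (Protocol 8.1.12).
- Scheduled tapers last 2, 3 or 4 weeks by dose reached (Protocol Tables 7-2 and 7-3). At the entry doses the tables give 28 days below 30 kg and 21 days in the two heavier bands.
- Assumption: the taper starts the day after Visit 13 or the ETV.

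**The plan's own day count.** 12 × 28 = 336, as SAP 3.2.5 states. The boundaries are then Days 84, 168, 336, 504 and 672, and 24 × 28 = 672 = 96 × 7.

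**Share of the whole period.** Share = T / (7w + T), with T taper days after leaving at Week w.

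| Leaving at | T = 14 | T = 21 | T = 28 |
|---|---|---|---|
| Week 12 (84 days) | 14/98 = 14.3% | 21/105 = 20.0% | 28/112 = 25.0% |
| Week 28 (196 days) | 14/210 = 6.7% | 21/217 = 9.7% | 28/224 = 12.5% |
| Week 96 (672 days) | 14/686 = 2.0% | 21/693 = 3.0% | 28/700 = 4.0% |

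**Share of one interval, early leaver.** With an ETV on Day 84 and a 28-day taper, the taper covers Days 85 to 112. These are the subject's only days in the >3 to ≤6 month interval (Days 85 to 168), so 28 of 28 are taper days. The same holds at Days 168, 336 and 504, and for an ETV shortly before a boundary if the taper crosses it.

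**Share of the ≥24-month interval, completer.** Counting 672 days on from Day 1 puts Visit 13 at Day 673, window Days 666 to 680. The interval is taken from Day 672.

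| Visit 13 | Pre-taper days | T = 14 | T = 21 | T = 28 |
|---|---|---|---|---|
| Days 666 to 671 | 0 | 100% | 100% | 100% |
| Day 673 | 2 | 14/16 = 88% | 21/23 = 91% | 28/30 = 93% |
| Day 680 | 9 | 14/23 = 61% | 21/30 = 70% | 28/37 = 76% |

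Starting the interval at Day 673, or treating the end of Week 96 as Day 672, removes one pre-taper day and raises the shares in the last two rows.

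**Illustration with assumed seizure rates (not from the documents).**
- If the percentage of seizure-free days is 20 points lower (range 10 to 40) during a 28-day taper, a completer's overall value falls by 0.04 × 20 = 0.8 points (0.4 to 1.6). For an ETV on Day 84 it falls by 0.25 × 20 = 5 points (2.5 to 10).
- Suppose a baseline of 10 seizures per 28 days, 4.8 before taper (a 52% reduction) and 9.6 during it. With an ETV on Day 84 the whole-period rate is (3 × 4.8 + 9.6) × 28/112 = 6.0, a 40% reduction, so the subject is no longer a 50% responder. For a completer it is (24 × 4.8 + 9.6) × 28/700 = 4.99, a 50.1% reduction, and the subject remains one.

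**The case against.** The strongest defence is that SAP 3.2.2 states its rule openly and taper days are on-drug days. Every scheduled taper dose lies within the range Protocol Table 7-1 allows during treatment (2 to 12 mg/kg/day, or 100 to 600 mg/day). Protocol Section 12 leaves analysis detail to the SAP. SAP 4.2.5 notes that efficacy is not the primary objective and that the setting is uncontrolled with individualised dosing. If seizures rise during taper, the SAP window is also the less flattering one.

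Much of this stands. It justifies the window for safety and exposure. The effect on a completer's overall value is small, and the ≥24-month interval is a residual one. An interval result from very few days also has a separate cause, the missing minimum in SAP 9.1.3: an untapered subject leaving on Day 86 still gets a >3 to ≤6 month result from two days.

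It does not justify using the same window for the seizure variables. The protocol ties the secondary variable to the Treatment Period and names the Taper Period separately, and SAP 3.9 is silent.

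A reader might also infer that Taper Visit results become Last Visit values, or that completer cohorts are inflated. The documents do not support this as a general defect. Under SAP 3.2.6 a Taper Visit qualifies only if dated on or before the end of the Treatment Period, and SAP 3.2.4 labels it separately. SAP 3.2.19 speaks of subjects treated with LCM, and taper days are treated days.

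**Conclusion.** The concern holds. Following the SAP as written, the only secondary efficacy variable and the whole-period responder, percent-change and seizure-free summaries include taper days, and interval results can rest on them entirely. Whole-period seizure-free status can change only for a subject who would otherwise qualify under SAP 3.2.18.

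The shares are per tapering subject and assume scheduled tapers and visits within window. They are not bounds, because Protocol 7.2.2 permits slower and faster tapers and Protocol 8.6 permits departures from the visit schedule. The number who taper and their seizure rate during taper are not given, so study-level size and direction are unknown.

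Three stronger readings go too far:
- **Biased headline result.** A reader might infer that the overall percentage of seizure-free days is materially biased. At 2 to 4% of a completer's days, with no data on taper seizures, the documents do not show that.
- **One subject in five affected.** With a 28-day taper, 5 × 28 = 140 of 672 possible leaving days (21%) give a next interval made only of taper days. This counts calendar days, not subjects, and includes cases with a single day past the boundary.
- **Compromised safety results or a compromised test.** Treatment-emergent events have their own rule, to 30 days after the last dose (SAP 8.2), and no hypothesis is tested.

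**What to change.** Keep the SAP 3.2.2 period for safety and exposure. For the seizure variables in SAP 9.1, with SAP 3.2.18, 3.2.20 and 3.2.21, end the window at the earlier of the Visit 13/Termination Visit or ETV and the last LCM dose. Where dosing records identify a taper that began before that visit, which Protocol 8.6 allows, end it on the last pre-taper day. Summarise or list taper diary days separately, and declare the wider safety window in SAP 3.9.

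The cost is one extra derived date. Neither document defines a first taper dose date or says how to tell a taper from a permitted dose decrease, so the early-taper clause works only where the records make it clear. A completer with a 28-day taper goes from about 700 to 672 days in the overall denominator. On-schedule tapering completers keep 0 to 9 days in the ≥24-month interval instead of 23 to 37, so it becomes nearly empty. A subject with an ETV on Day 84 leaves the >3 to ≤6 month interval. The safety and exposure tables lose no data.

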#### Post-Treatment Period

This is defined as the period of time from the day after the end date of the Treatment Period and extending through to the Final Clinic Visit or last contact with the subject.

### 3.2.3 Mapping of assessments performed at Early Termination Visit

Safety and efficacy assessments at an ETV that correspond to a scheduled visit will be summarized at the scheduled visit corresponding to the ETV if the assessment was scheduled to occur at that visit. Such assessments will also be considered for Last Visit.

Subjects who prematurely discontinue the study will be evaluated based on the data collected at each visit attended. For those subjects, the ETV will be mapped to the next scheduled visit, ie, the assessments documented at ETV will be assigned to the next scheduled visit, for which the corresponding assessment is scheduled following the last documented visit.

In particular, assessments which are done at all visits during the Treatment Period (eg, vital signs, body weight and height) will have ETVs corresponding to a scheduled visit mapped to the corresponding scheduled visit.

### 3.2.4 Study visit labeling

Visits will be labeled in table summaries (according to the schedule outlined in Section 5.2 of the protocol) as follows:

- "Visit X, Week X" for scheduled visits during the Treatment Period

- “Taper Visit”
- “Safety Follow-up Visit”
- “Last Visit” (see below in [Section 3.2.6](#) for further information)

Listings will also include “Unscheduled Visit” as applicable.

### 3.2.5 Monthly time intervals

A month is defined as 28 days and time intervals based on monthly durations are defined as multiples of 28 days (eg, 12 months is defined as 336 days). The definition of 3-month intervals is based on the example durations in [Table 3–1](#) which use 28-day months where the date of the first dose of LCM is Day 1:

**Table 3–1: Definition of monthly interval durations during the first year**

Interval	Duration Definition
Months 1 to 3	Days 1 to 84
Months 4 to 6	Days 85 to 168
Months 7 to 9	Days 169 to 252
Months 10 to 12	Days 253 to 336

Subsequent 3-month intervals are defined in a similar manner.

For the analysis of safety outcomes in the Treatment Period, a subject is included in the analysis for a 3-month interval if they are exposed to LCM at any time during that interval.

### 3.2.6 Last Visit

The Last Visit for all assessments in EP0034 is the last non-missing assessment during the Treatment Period. All scheduled and unscheduled assessments within this time period will be considered. Last Visit will be determined separately for each study procedure where Last Visit is mentioned within this document.

### 3.2.7 Exposure duration

The overall duration of LCM exposure for each subject will be calculated as the date of the last dose of LCM minus the date of the first dose of LCM plus 1 day. Gaps in treatment or days with unknown dosing will not be subtracted from the duration of exposure. The duration of LCM exposure will be summarized, separately, as a continuous parameter (in days) and as a categorical parameter, where categories will be defined using the following cumulative 6-month intervals for the Treatment Period: >0 months, >6 months, >12 months, >18 months, and >24 months.

Subject-years of LCM exposure in the study is calculated as the duration of exposure (days) divided by 365.25. Subject-years of LCM exposure will be summarized using the following cumulative 6-month time intervals for the Treatment Period: >0 months, >6 months, >12 months,

>18 months, and >24 months, where 1 month is defined as 28 days.

### 3.2.8 Modal and maximum daily LCM dose

The modal daily LCM dose (mg/kg/day) is defined as the daily LCM dose the subject received for the longest duration during the Treatment Period in EP0034.

The maximum daily LCM dose (mg/kg/day) is defined as the highest total daily dose a subject received during the Treatment Period in EP0034.

Maximum daily LCM dose will be summarized as a continuous parameter (in mg/kg/day). Modal daily LCM dose will be summarized as a continuous (mg/kg/day) and categorical parameter, using the following categories (mg/kg/day) for the Treatment Period: 0.0 to <4.0,

$\geq 4.0$  to <6.0,  $\geq 6.0$  to <8.0,  $\geq 8.0$  to <10.0,  $\geq 10.0$  to <12.0, and  $\geq 12.0$ . This will require that tablet doses in mg/day be converted to mg/kg/day. The following steps will be applied:

1. For days for which a subject received oral solution, the total daily dose in mg/kg/day will be classified into 1 of the above categories on a daily basis.
2. For days for which a subject received tablets, the total daily dose in mg/day will be converted to mg/kg/day by dividing the total daily dose in mg/day by the most recently available body weight; the derived dose in mg/kg/day is then classified into 1 of the above categories on a daily basis.
3. Once all total daily doses are converted to mg/kg/day and classified into 1 of the above categories, the modal daily dose is the dose category which was most frequent.

Should subjects receive both oral solution and an oral tablet on the same day, then the individual tablet dose in mg is converted to mg/kg by dividing by the most recently available body weight, and then the individual dose of oral solution in mg/kg is added to the tablet dose in mg/kg to obtain a total daily dose in mg/kg/day.

The modal and maximum daily dose calculations are based on the number of days a subject was on a given daily dose. Gaps in LCM dosing will be excluded from the determination of modal and maximum daily dose (ie, no imputation for days with missing dosing log information will be performed). If a subject was on two different LCM doses for the same duration of time (ie, a tie when calculating modal daily dose), the modal daily dose will be set to the lower of the doses.

For efficacy analyses related to seizure frequency, modal daily LCM dose will be presented as the most frequent dose during the interval of observation for seizure frequency parameters.

In summary tables and listings, modal daily dose will be presented with the following column headers: <4mg/kg/day to represent doses from 0 to <4.0mg/kg/day, 4mg/kg/day to represent doses 4.0 to <6.0mg/kg/day, 6mg/kg/day to represent doses 6.0 to <8.0mg/kg/day, 8mg/kg/day to represent doses 8.0 to <10.0mg/kg/day, 10mg/kg/day to represent doses 10.0 to <12.0mg/kg/day, and  $\geq 12$  mg/kg/day to represent doses greater than or equal to 12.0mg/kg/day.

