## 8.1 Extent of exposure

All the summaries described below will also be presented for the FAS.

The duration of LCM exposure (days), as defined in [Section 3.2.7](#), will be summarized as a continuous parameter (in days) overall, and repeated by weight band using the levels defined in [Section 3.2.10](#). In addition, the duration of LCM exposure will be summarized using the cumulative 6-month time intervals for the Treatment Period, as defined in [Section 3.2.7](#).

Subject-years of LCM exposure will be summarized using the cumulative 6-month time intervals for the Treatment Period, as defined in [Section 3.2.7](#).

The maximum daily LCM dose (mg/kg/day), as defined in [Section 3.2.8](#), will be summarized overall, and repeated by weight band using the levels defined in [Section 3.2.10](#).

The modal daily LCM dose (mg/kg/day), as defined in [Section 3.2.8](#), will be summarized, overall, and repeated by weight band using the levels defined in [Section 3.2.10](#). In addition, the number of subjects and subject-years exposed in each of the modal daily LCM dose categories (mg/kg/day) will be summarized for the Treatment Period, as defined in [Section 3.2.8](#).

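### SAP 3.2.8 gives two rules for modal daily dose, so a child's continuous modal dose can fall outside its own modal category; for tablets, weight updates add to the problem

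*SAP*

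**What the plan says.** SAP 3.2.8 opens at the level of the dose: the modal daily dose "is defined as the daily LCM dose the subject received for the longest duration during the Treatment Period in EP0034". It then plans two summaries: "Modal daily LCM dose will be summarized as a continuous (mg/kg/day) and categorical parameter", with six categories. Three steps follow. Oral-solution days are classified by their mg/kg/day dose. Tablet days are first converted "by dividing the total daily dose in mg/day by the most recently available body weight" and then classified. Step 3 concludes that "the modal daily dose is the dose category which was most frequent".

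The section then returns to the dose level: "The modal and maximum daily dose calculations are based on the number of days a subject was on a given daily dose". If two doses tie, "the modal daily dose will be set to the lower of the doses". No rule says how a continuous value follows from a modal category, or that the category must contain the continuous value. The section gives no number of decimals for a converted tablet dose.

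SAP 8.1 uses these quantities for the SS and repeats them for the FAS. The modal dose is summarized overall and by weight band, and "the number of subjects and subject-years exposed in each of the modal daily LCM dose categories (mg/kg/day) will be summarized".

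**The concern.** Two rules for one derived variable can return two answers for the same child, and both answers would be reported side by side as that child's modal dose.

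The tablet conversion is a separate mechanism. Protocol 7.2 has weight checked at every visit, so in a growing child each visit can start a new mg/kg/day value although the prescribed tablets have not changed. The longest-held value may then mark the longest gap between visits and not the dose taken for longest. Gaps widen from 4 to 8 to 12 weeks, and the 12-week gaps all lie after Week 60.

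At stake is whether the exposure tables describe correctly the doses behind the long-term safety data. Where the rules conflict, a programmer would have to choose between them without guidance.

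**Working it through.** The documents give no figure on this point, so there is none to reproduce. I applied both rules, as written, to the same day-by-day dose records.

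**Inputs from the documents**
- Visits at Weeks 0, 4, 8, 12, 20, 28, 36, 44, 52, 60, 72, 84 and 96 (SAP 2.3): 96 × 7 = 672 days.
- Categories <4, 4 to <6, 6 to <8, 8 to <10, 10 to <12 and ≥12 mg/kg/day, with ties to the lower dose (SAP 3.2.8).
- Tablet conversion: mg/day ÷ latest weight.

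**Assumptions:** the dose histories, starting weights and growth below are illustrative, with visits exactly on schedule.

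**Rule A** is the longest-held value. **Rule B** is the most frequent category.

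**Record 1: oral solution, no weight conversion.** 10 mg/kg/day for 252 days, 9 for 224, 8 for 196.
- Rule A: 10 (252 days is the longest run), which lies in 10 to <12.
- Rule B: 8 to <10, with 224 + 196 = 420 of 672 days.
- The continuous mode lies outside the modal category.

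**Record 2: tablets, dose raised.** 50 kg at entry, gaining 4 kg/year; 300 mg/day to Week 60 (420 days), then 400 mg/day (252 days). Weight at week w = 50 + 4 × 7w/365.25.
- On 300 mg/day the value falls from 300/50 = 6.00 at Week 0 to 300/53.99 = 5.56 at Week 52. No single value lasts longer than 56 days.
- On 400 mg/day: 400/54.60 = 7.33, 400/55.52 = 7.20 and 400/56.44 = 7.09, each for 84 days.
- Rule A: three values tie at 84 days and the lowest, **7.09**, is taken. It comes from the dose held for 252 of 672 days.
- Rule B: **4 to <6**, with 420 − 28 = 392 of 672 days (the first 28 days, at 6.00, fall in 6 to <8).
- Rounded to 1 decimal, the 300 mg/day values merge. 5.8 and 5.6 each cover 112 days, while 7.3, 7.2 and 7.1 cover 84 each. Rule A then gives **5.6**, inside 4 to <6 and from the longer-held dose. The disagreement disappears.

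**Record 3: tablets, dose lowered.** 300 mg/day to Week 84 (588 days), then 200 mg/day (84 days), weight rising linearly over 96 weeks.

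| Weight | Rule A, 2 decimals | Rule A, 1 decimal | Rule B |
|---|---|---|---|
| 50, unchanged | 6.0 | 6.0 | 6 to <8 |
| 50 to 54 kg | 3.74 | 5.7 | 4 to <6 |
| 50 to 58 kg | 3.51 | 5.5 | 4 to <6 |
| 50 to 62 kg | 3.31 | 3.3 | 4 to <6 |
| 40 to 50 kg | 4.10 | 4.1 | 6 to <8 |

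With two decimals, every record with weight gain takes its continuous mode from the 200 mg/day dose, held for 84/672 = 12.5% of days. One-decimal rounding restores agreement in two of the four records with weight gain.

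**Subject-years.** SAP 3.2.7 computes subject-years from total exposure duration. SAP 8.1 tabulates them by modal category without saying how a subject's days at other doses are counted.

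**The case against.** The strongest reply is that the two rules serve different tables: the opening definition feeds the continuous summary and steps 1 to 3 feed the categorical one. The mode of values and the mode of bins need not coincide. That is a possible reading, but the SAP does not state it, and Record 1 shows that under it one child still carries two conflicting modal doses.

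Four stronger readings are tempting and the documents do not support them.

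- *A tablet-taker's continuous modal dose always reflects the last third of the study.* Not so. It need not when weight is unchanged, when the child leaves before the 12-week gaps begin, or when one-decimal rounding merges values. The exact ties in Record 3 also become uncommon with the ±7-day visit window in Protocol 8.
- *About a quarter of tablet-takers are affected.* A simulation (assumed 50 to 75 kg, gaining 1 to 6 kg/year, one change from 300 to 200, 400 or 500 mg/day) gives roughly 23 to 25%, both for a value outside the category and for one from a dose not held longest. That requires every child to change dose and complete 96 weeks, with unrounded doses. If only a quarter change dose and one decimal is kept, the figures are about 8% and 5%. No document gives a dose-change rate.
- *All of a subject's years are credited to the modal category.* SAP 8.1 does not say this; it gives no attribution rule.
- *The modal and maximum dose tables are the only dose information planned.* SAP 3.1 and 7 also plan listings of documented, calculated and dispensing data.

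It is also fair that the consequence is limited. SAP 3.6 no longer groups summaries by modal dose (removed in Amendment 3). The primary safety variables and seizure-free days do not depend on it.

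**Conclusion.** The derivation is wrong as written, but the point is minor. The conflict between the two rules needs no assumption about growth or rounding; Record 1 is enough to show it. The tablet effect is real but conditional: its presence and size depend on weight gain, dose changes, visit gaps and a rounding convention that SAP 3.2.8 does not state. I therefore put no overall frequency on it. A child on one stable mg/kg/day dose is unaffected. The reach is the descriptive exposure tables in SAP 8.1, where the continuous and categorical modal doses can contradict each other and the subject-years by category cannot be interpreted until the attribution is stated. Nothing here bears on which dose a child should receive.

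**What to change.** In SAP 3.2.8, use one rule:

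1. Identify the longest-held dose on the prescribed regimen, so that a weight update alone does not create a new tablet dose.
2. Express that dose in mg/kg/day with one named reference weight and a stated number of decimals.
3. Handle a change of formulation at the same total daily mg dose, and days on both formulations, by total daily dose. Finding the mode in mg/day for tablets and mg/kg/day for solution without this step would split one dose into two.
4. Read the category from that single value, in place of step 3.

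In SAP 8.1, report subject-years by actual daily dose category, summing the days already classified in steps 1 and 2. Alternatively, state that each subject's total exposure is assigned to the modal category.

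Cost: SAP wording and one derivation; no new data.
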